5-24-2021

Pharmacologically-based Strategies for Opioid Substitution Therapy During Pregnancy

PRO18070495 / STUDY19100128

NCT03831113

Protocol version 1.8

The Eunice Kennedy Shriver National Institute of Child Health and Human Development (NICHD)

Principal Investigator:

[name]
Magee-Womens Hospital
[name]
[name]

Specific Aim 4

Specific Aim 4 compares dose reduction strategies for Suboxone or Subutex in pregnancy that are based on the pharmacodynamic and pharmacokinetic characteristics of BUP.

a) Primary Research Questions

1. Is adherence during dose reduction influenced by the magnitude or frequency of a given dose reduction?
2. Is adherence during dose reduction influenced by dosing frequency?
3. Does mu receptor sensitivity change during dose reduction?

b) Eligibility Criteria

Inclusion Criteria – must meet all of the following:

1. On a stable BID, TID or QID dosing regimen of BUP for at least 2 weeks as part of an established medication- assisted treatment (MAT) program.
2. Willingness to undergo supervised dose reduction
3. Subjects on BID, TID or QID dosing, willing to be assigned to the Magnitude, Frequency, or Dosing group, depending on their current dosing
4. Single gestation between 14-30 weeks at the initiation of dose reduction
5. On a BUP dose between 6- 24 mg daily (lower doses will not provide sufficient data points)
6. Willingness to have urine samples tested for drugs of abuse and blood samples tested for BUP+M concentrations during the Medical Supervised Withdrawal (MSW) clinic appointments
7. Willingness to attend weekly or biweekly MSW clinic appointments and to have daily contact via text messaging to complete daily logs of sleep quality, withdrawal symptoms and symptoms of craving. Subjects may consent to receiving daily text messages with a link to a REDCap where they can complete the daily questionnaires electronically. Alternatively, they may complete hard copies of the questionnaires and return them during their weekly clinic visits.
8. Willingness to attend psychosocial support meetings, as needed.

Exclusion criteria – cannot meet any of the following:

1. Current use of cocaine, heroin, benzodiazepines, barbiturates, phencyclidine (PCP), or opioids other than BUP
2. Currently taking more than two mental health medications

3. Active moderately severe depression (PHQ-9 score ≥ 15 or suicidal ideation)
4. Current incarceration

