- Subjects in the BID group will be assigned to the Dosing group. The Dosing group may follow the Magnitude (alternating 1 mg and 2 mg dose reductions weekly) or Frequency (2 mg dose reductions on alternating intervals of 1 and 2 weeks) dose reduction schedules.

In all groups, the alternating approach will continue until the subject is Suboxone or Subutex free or at the lowest dose tolerable. We appreciate that some subjects may not tolerate the recommended dose reduction especially at the lower doses. Subjects that experience withdrawal symptoms may be treated with ancillary medications such as Benadryl or clonidine. To minimize any risk of relapse, subjects who are intolerant to a given reduction will be allowed to go back to the last tolerated dose taken prior to the reduction. Visual Analog Scale (VAS) scoring will document their intolerance and this, combined with pharmacological data from the subject, will inform our development of an optimized pharmacological approach to dose reductions. After the subject has been on the higher dose for one week we will re-initiate the dose reduction strategy to which she was assigned. We will repeat this process one more time and if she remains intolerant to further dose reductions, we will not attempt further reductions but rather will maintain her on her current dose. If the subjects desires additional attempts at dose reduction, we will accommodate her request. At this time, she may elect to re-initiate the original dose reduction strategy or select an alternative reduction strategy. For all subjects, we will continue the surveillance approach we have in place throughout the pregnancy, delivery, and into the postpartum period.

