Since our focus is to assess whether the magnitude of the dose change, frequency of dose change and dosing frequency impact adherence during reduction, this pharmacodynamic study will be completed when the subjects are off BUP entirely or on the lowest tolerable dose. However, we will continue to see the subjects weekly or biweekly, monitor their adherence and continue to provide counseling sessions, as needed, until the 6-week postpartum visit. We will also evaluate peripheral blood mononuclear cells (PBMCs) as a surrogate marker of metabolic enzymes and transporters. The expression of drug metabolizing enzymes and transporters in the PBMCs will be correlated with the plasma concentrations of BUP and its major metabolites. Two maternal blood samples will be drawn for PBMC analysis; one during pregnancy and one in postpartum. The first sample will be drawn during the Pre-Study Screening; however, if this is not possible, it may be drawn at any time during pregnancy. The second sample will be drawn at 4-6 weeks postpartum, but as close as possible to the 6-week postpartum visit.

For subjects not enrolled in specific aim 3a or 3b, we will collect a cord blood sample at the time of delivery as well as maternal and newborn hair within 3 days of delivery, when possible. An additional cord blood sample (10 mL) will be drawn for genetic studies related to metabolizing enzymes, if the mother consents. The minimal amount of hair needed is 20 mg but we will ask for 100 mg which is still a very small amount. Hair will be removed from the mothers and baby's head (if consent is granted). Mother will decide where the hair will

be removed from her and her baby. The collection of these samples will be described in full detail during the consent process.

Note: Subjects that consent to participate in specific aims 3 (Parts 1 or 2) will already have the cord blood and hair samples collected as part of that specific aim. The collection of these biological samples only applies to those subjects not already enrolled in specific aim 3.

Table 1.

Dose Reduction Schedules if Start Dose is 16 mg Daily			
Group	Frequency	Magnitude	Dosing
Strategy	Reduce dose by 2 mg weekly then biweekly, repeat till dose=0 or at the lowest possible dose	Reduce dose by 1 and then 2 mg weekly, repeat above till dose=0 or at the lowest possible dose	May elect either the Frequency or Magnitude dose reduction schedule.
Dosing Frequency	QID or TID	QID or TID	BID
Dose			

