Week 1	16	16	Refer to the appropriate dose schedule in the Frequency or Magnitude columns
Week 2	14	15	
Week 3	14	13	
Week 4	12	12	
Week 5	10	10	
Week 6	10	9	
Week 7	8	7	
Week 8	6	6	
Week 9	6	4	
Week 10	4	3	
Week 11	2	1	
Week 12	2	0	
Week 13	0	0	

e) Statistics

The outcome(s) of interest are the pharmacodynamic endpoints that reflect the acclimatization of the mu receptors and opioid-affected brain functions. Each subject in a group will undergo alternating treatments to minimize any between subject differences that would impact the response to the decrease in dose. In this study, we will rely on scores from the self-administered VAS questionnaires. We will determine both an average and highest value for each of the VAS questionnaires weekly. The average values over the 7 days of

that given dose from the VAS questionnaires will be combined to create a single score for each week. A similar approach will be taken for the highest rather than average values. Based on the study of Dunn et al ^{46,47}, the mean value for the withdrawal VAS questionnaire (scale 1-10) in non-pregnant subjects was 30 with a standard deviation of ~25. These values are estimates since graphs were provided but not tabular data. A difference of 25% in the VAS combined scores between any of the comparisons would seem clinically meaningful. Thus, a sample size of 10 in each group is sufficient to detect a difference in VAS scores between any of the comparison groups. The comparisons in the Frequency group will be VAS scores between the 1 vs 2 week reductions. The comparisons in the Magnitude group would be VAS scores between the 1 and 2 mg reductions. The comparison in the Dose group will be a comparison of the VAS scores during the 1 mg and 2 mg reductions. Also, VAS scores in the Dose group will be compared to the VAS scores in the Magnitude group both at the 1 and 2 mg reductions. The change in mu receptor sensitivity will be determined by comparing the BUP+M

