Recruitment of subjects for specific aim 4, dose reduction may prove challenging since we have not offered this option previously at Magee; however, we performed a survey recently of potential candidates for dose reduction and detoxification and the response was very encouraging. Of 40 women asked if they would consider dose reduction or detoxification, more than 50% said they would be interested. Recruitment for specific Aim 1 may be challenging because the subject will need to be willing to allow withdrawal to occur in addition to spending time in the CRC. Time in the CRC has been an ongoing challenge to recruitment in all OPRU studies. Given that all the MAT clinic staff have been involved with our BUP research in the past and 2 BUP writers are supported by this grant, I am confident that we can recruit sufficient subjects to complete these aims.

F. Potential Problems & Alternative Strategies

For all specific aims, recruitment must be considered. Although this is unlikely to be problematic given our large population, it may be an issue. If recruitment is slower than required to achieve our goals, we will approach other research-oriented centers with a large opioid using population to assist in recruitment.

For specific aim 4, possible problems include high drug withdrawal and craving on the lowest dose reduction and a high dropout rate. The possibility that even the lowest dose reduction will lead to unacceptable rates of dropout and study withdrawal rates is not likely given the reasonable dose reduction rates reported by others with dose reductions much greater than those proposed. If this does indeed happen then we would target an even slower rate of reduction.

G. Subject Removal Criteria

For specific aim 4, if heroin, cocaine, benzodiazepines, barbiturates, phencyclidine (PCP), or opioids other than BUP are detected in the urine during the pre-study screening or at any time during the study, or if the urine drug screen results from the MAT clinic are positive at any time during her dose reduction, she will be dropped from the study and replaced. Subjects who do not return their residual drug on more than 3 occasions will be withdrawn from the study.

H. Clinical Data Management

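### Section G withdraws women at a fixed count of unreturned drug, so it selects on behaviour close to the adherence outcome; the size of the effect cannot be determined from the protocol

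*Combined protocol and SAP*

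**What the plan says.** Section G has two removal rules. One, expressly for Aim 4, drops and replaces women with positive urine tests and is not the subject here. The other reads: "Subjects who do not return their residual drug on more than 3 occasions will be withdrawn from the study". It names no aim, gives no definition of an occasion, and is silent on replacement and on the withdrawn woman's data. Residual drug appears nowhere else in the document: not in the eligibility criteria, the visit procedures or the Statistics section.

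Primary question 1 is "Is adherence during dose reduction influenced by the magnitude or frequency of a given dose reduction" and question 2 is "Is adherence during dose reduction influenced by dosing frequency". Section d) repeats that "our focus is to assess whether the magnitude of the dose change, frequency of dose change and dosing frequency impact adherence during reduction", and says that daily adherence will be compared within and between the groups. Section e) defines no adherence measure; it says "In this study, we will rely on scores from the self-administered VAS questionnaires". Section d) also promises "For all subjects, we will continue the surveillance approach we have in place throughout the pregnancy, delivery, and into the postpartum period", with visits to 6 weeks postpartum.

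**The concern.** Repeatedly failing to bring back unused drug is information about adherence. Withdrawing women for it removes some of the least adherent from a study that asks what drives adherence. With 10 women per group, a few such losses matter.

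The threshold is also a count and not a proportion. A woman with many return occasions has more chances to reach four than a woman with few. A woman who does not tolerate a step goes back to the previous dose for a week before restarting, so women who are struggling accumulate more occasions. The weeks lost run from removal to the end of the taper. They therefore always include the low-dose end, where section d) itself expects intolerance. Withdrawal from the study is not reconciled with the promise of continued surveillance for all subjects.

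**Working it through.** **Inputs from the protocol.** Removal at the 4th non-return (section G). Starting dose 6 to 24 mg daily (section b). Magnitude rule: "Reduce dose by 1 and then 2 mg weekly, repeat above till dose=0 or at the lowest possible dose". Frequency rule: 2 mg steps at alternating intervals of 1 and 2 weeks (Table 1). Visits weekly or biweekly, timed by the healthcare provider (section d). Ten women per group (section e).

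**Assumed, not in the protocol.** One return occasion per visit; a probability p of a missed return, taken from 0.05 to 0.30.

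**Step 1: taper lengths.** Applying the two rules from 16 mg reproduces both columns of Table 1 week by week: zero is reached after 11 weeks (Magnitude) and 12 weeks (Frequency). The same rules give 4 and 4 weeks from 6 mg, and 16 and 18 weeks from 24 mg. These lengths exclude step-backs, each of which adds at least a week.

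**Step 2: chance of removal, independent misses.** For n occasions,

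P(removed) = 1 − Σ (k = 0 to 3) C(n,k) p^k (1−p)^(n−k).

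For n = 12 and p = 0.2: 1 − (0.0687 + 0.2062 + 0.2835 + 0.2362) = 0.205.

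| Occasions | p = 0.05 | p = 0.10 | p = 0.20 | p = 0.30 |
|---|---|---|---|---|
| 4 (6 mg, weekly) | 0.001% | 0.01% | 0.16% | 0.8% |
| 6 (12-week taper, biweekly) | 0.01% | 0.13% | 1.7% | 7.0% |
| 11 (16 mg Magnitude, weekly) | 0.2% | 1.9% | 16.1% | 43.0% |
| 12 (16 mg Frequency, weekly) | 0.2% | 2.6% | 20.5% | 50.7% |
| 16 (24 mg Magnitude, weekly) | 0.7% | 6.8% | 40.2% | 75.4% |
| 18 (24 mg Frequency, weekly) | 1.1% | 9.8% | 49.9% | 83.5% |

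A 6 mg taper with biweekly visits has 2 occasions, so the rule cannot be met during it. Two extra weeks on a 16-occasion taper, as two step-backs could add, raise removal from 40.2% to 49.9% at p = 0.2 and from 6.8% to 9.8% at p = 0.1.

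**Step 3: misses that cluster within women.** Let p vary between women as a beta distribution with mean 0.20 and intraclass correlation ρ (a = 0.2(1−ρ)/ρ, b = 0.8(1−ρ)/ρ). The beta-binomial chance of four or more misses is:

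| ρ | 4 occasions | 6 | 12 | 18 |
|---|---|---|---|---|
| 0 (independent) | 0.16% | 1.7% | 20.5% | 49.9% |
| 0.3 | 3.3% | 10.8% | 27.6% | 37.6% |
| 0.6 | 9.3% | 16.4% | 25.2% | 29.5% |
| 0.9 | 17.1% | 19.4% | 21.4% | 22.3% |

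The gap by taper length narrows as clustering grows.

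**Step 4: what losses would cost.** The sample sizes in section e) (25, 15, 10, 7) are reproduced exactly by an unpaired t-test with SD 25, differences of 15% to 30% of 120, one-sided 5% and 80% power. The plan states none of the last three settings, and other combinations come close. On that inferred basis, power is 82.5% with 10 per group and 73.8% with 8. Two losses per group, unreplaced, is what 20.5% removal would mean (10 × 0.205 = 2.05).

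**The case against.** **Scope.** The sentence names no aim, while the one before it opens with Aim 4. Section E refers to four aims and only Aim 4 is described here, so the rule may have been meant for another aim. This is a fair doubt. As written, though, the sentence is unrestricted and covers Aim 4.

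**Size.** The miss rate, the meaning of an occasion and independence are all assumptions. At p = 0.05 removal is about 1% or less on any uncomplicated taper. A reader might infer from the right-hand columns of the Step 2 table that long tapers will lose far more women than short ones; the documents do not establish that. Clustering weakens this contrast but not the selection itself, since the women removed are then the persistent non-returners.

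**Schedule bias.** A reader might also infer that the slower Frequency schedule is penalised relative to Magnitude. The two differ by no weeks at 6 mg and one week at 16 mg (16.1% against 20.5% at p = 0.2). Visit interval is set by the provider and not by group, and the main Magnitude and Frequency contrasts are within the same woman. This reading is not supported. Question 2 and the planned comparison of the Dosing with the Magnitude group are between women, so selective loss can still affect those.

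**Meaning of non-return.** The protocol does not make drug return its adherence measure, and a woman who took every dose may have nothing left to bring. This stands: non-return is close to adherence but is not the same thing.

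**Data already collected.** Nothing says that data before withdrawal are discarded, and with weekly visits a Magnitude woman has had both step sizes by her fourth visit. That limits the loss to later weeks; it does not remove it.

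**Conclusion.** The point holds as a design weakness of unknown size. That the rule is a fixed count, that it acts on behaviour close to the subject of questions 1 and 2, and that exposure to it rises with starting dose, visit frequency and step-backs all follow from the text, on the reading that return occasions track visits. How many women would go does not follow. Under independence, the plausible span over 12 to 18 occasions runs from 0.2% to 84% as p goes from 0.05 to 0.30, and the dependence on taper length weakens with clustering. The conclusion also assumes that drug return takes place in Aim 4, which no visit procedure confirms.

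**What to change.** Amend section G so that non-return does not end study follow-up or take a woman out of the analysis.

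- Define an occasion, and record each expected return as returned, nothing left to return, or not returned. The middle category avoids misclassifying women who used all their drug.
- Report non-return as an adherence measure by dose interval.
- Keep all VAS, urine and BUP+M data, including those after the fourth non-return.
- Leave any drug-accountability or dispensing consequence for the sponsor to set, separately from study withdrawal. The rule may serve such a purpose, so deleting it without saying what happens instead would go too far.
- If drug return is not done in Aim 4, remove the sentence or limit it to the aim it belongs to.

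The cost is a minor amendment and one case report form item, since visits already run to 6 weeks postpartum. The downside is that dose-taking will be uncertain in some intervals; the weekly or biweekly plasma BUP+M shows this only in part.
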